Lingual Endurance Exercise in Treating Post-Stroke Dysphagia NCT05523973

Last Institutional Review Board Approval Date: 2/18/25

Study Protocol

All procedures and study team members were approved by University of Cincinnati Institutional Review Board (IRB# 2022-0218). A convenience sample of participants were recruited from word-of-mouth referrals (e.g. UC stroke team) and information flyers that were distributed locally throughout the community and at other institutions in the area. Participants were eligible to participate if they had a history of ischemic stroke, were 21 years of age or older, at least 3 months since initial ischemic stroke, and able to follow 2 step directions. Exclusion included any history of dysphagia prior to the ischemic stroke, if participant was pregnant, or had a history of temporomandibular joint disorders. Final eligibility for full protocol enrollment included at least one impaired oral component score according to the MBSImP (Modified Barium Swallow Impairment Profile). This was judged at time of initial visit in the fluoroscopy suite by an MBSImP trained speech language pathologist (SLP).

Study Visits

This study used a prospective quasi-experimental design, with pre-test and post-test measures. Study visits included an initial in-person baseline visit with patient reported outcome measures (Swallowing Quality of Life Questionnaire, SWAL-QoL, and Eating Assessment Tool, EAT-10) and a modified barium swallow study (MBSS) followed by 8-10 weeks of at home lingual exercise with use of the TongueometerTM device. Weekly virtual visits completed with a license speech language pathologist. At the end of the 8-10 weeks participants came for an in person visit for post-treatment data collection. Participants were asked to complete lingual presses based on 75% repetitions at 50% of their maximum isotonic press. Participants were assigned to complete this task 3 times per day. Half of the participants were instructed to complete this task 2 times a day and once a day to do 10 effortful swallows with feedback from the device. Post-treatment data were collected at a final study visit where the same PROs were administered (SWAL-QoL, EAT-10) along with a post-treatment MBSS. Procedural details for study visits and exercises described below:

Modified Barium Swallow Study

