Descriptive statistics were calculated on all variables. Frequencies and percentages are reported for categorical variables. The normality of continuous variable distributions were assessed using histograms and box plots. For normally distributed continuous variables, means and standard deviations are reported, while . medians and interquartile ranges are provided for non-normally distributed continuous variables.

To examine treatment effects, differences in baseline measures from pre-treatment to post treatment were calculated, including EAT-10 scores; IOPI measures: average swallow pressure (kPa) over 3 trials, maximum effortful pressure (kPa) over 3 trials, maximum anterior max strength (kPa) over 3 trials, anterior isometric endurance max (seconds), and maximum anterior isotonic endurance (reps); maximum posterior strength (kPa) over 3 trials, posterior isometric endurance max (seconds), posterior isotonic endurance max (reps); MBSImP Oral Total scores, MBSImP Pharyngeal Total scores; and Swallowing Quality of Life questionnaire scores (SWAL-QOL), including overall total score, eating duration, food selection, fear, and fatigue; and ASPEKT measures, including Swallow reaction time, Pharyngeal swallow duration, UES opening, Laryngeal vestibular closure reaction time, Laryngeal vestibular closure duration, Preswallow residue, Vallecular residue, Pyriform sinus residue, Other residue, Pharyngeal area at max constriction, Maximum opening of UES, and Peak hyoid movement.

Linear regression models were used to examine differences in baseline measures from pretreatment to post treatment. Treatment group (Endurance only vs Endurance plus transference) and baseline measures were included as covariates. Models were evaluated for parsimony. Treatment group effects that were not statistically significant were eliminated from the model and re-evaluated. Residuals were examined to assess model fit. Bowker's test of symmetry was used to test for differences in PAS score category and FOIS from pre- to post-treatment. Cohen's d was used to calculate effect sizes. Statistical significance was determined at p-values less than 0.05. All analyses were conducted using SAS version 9.4 (SAS Institute, Cary, NC).

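### The plan does not say which regression parameter, or which baseline value, tests pre-post change; at the sample mean baseline the standard error understates uncertainty about population mean change unless the post-on-pre slope is 1

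*Combined protocol and SAP*

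**What the plan says.** All references are to the Statistical analysis section unless stated otherwise.

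- Outcome: "To examine treatment effects, differences in baseline measures from pre-treatment to post treatment were calculated". The dependent variable is therefore a change score.
- Model: "Linear regression models were used to examine differences in baseline measures from pretreatment to post treatment".
- Covariates: "Treatment group (Endurance only vs Endurance plus transference) and baseline measures were included as covariates".
- Model reduction: "Treatment group effects that were not statistically significant were eliminated from the model and re-evaluated".
- Threshold: "Statistical significance was determined at p-values less than 0.05". Sidedness is not given.
- Ordinal outcomes: Bowker's "test of symmetry was used to test for differences in PAS score category and FOIS from pre- to post-treatment".
- Design, from Study Visits: "This study used a prospective quasi-experimental design, with pre-test and post-test measures". Both groups exercise and no untreated group is described.

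The continuous outcomes listed are EAT-10 (1), IOPI measures (8), MBSImP totals (2), SWAL-QOL scores (5) and ASPEKT measures (12), which makes 28. The section does not name the coefficient, contrast or least-squares mean that tests change. It does not say whether baseline is centred or at what baseline value change is evaluated.

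**The concern.** With no untreated group, pre-post change carries the treatment-effect claim. When the group term drops out, the fitted model is change = a + b × baseline. Unless b is 0, this gives a different change at each baseline value, so the model has no single result for change until a baseline value is chosen. A reader of the p-values cannot tell which null hypothesis each one tests.

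The choice also affects the error rate. The obvious candidate is change at the sample mean baseline. It reproduces the raw mean change, but the regression attaches an SE that treats the observed mean baseline as fixed. If the intended statement is about patients like those sampled, that SE leaves out one source of variation, and the nominal 5% level may not hold.

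**Working it through.** **Inputs.** From the plan: significance level 0.05, change score as outcome, baseline as covariate, group dropped if not significant. Assumed, because the documents give none of them: sample size N, post/pre SD ratio k, pre-post correlation r, normal data, no true mean change, two-sided testing. The plan states no SE or power figure, so there is none to reproduce.

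**Formula.** Let B be the slope of post on pre, s² the residual variance and V the baseline variance.

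- Estimate at the sample mean baseline: the raw mean change.
- SE from the regression: √(s²/N).
- SE of the mean change over repeated samples: √([s² + (B−1)²V]/N).

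Set V = 1, so that B = kr and s² = k²(1−r²). Then s² + (B−1)² = k² − k²r² + k²r² − 2kr + 1 = 1 + k² − 2kr, and

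SE ratio (regression / paired) = √[k²(1−r²) / (1 + k² − 2rk)].

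The ratio is 1 only when kr = 1. At k = 1 it reduces to √((1+r)/2).

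**Equal SDs (k = 1).** Simulated errors are for N = 20, with at least 20,000 replicates per setting and the range across runs shown.

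| r | SE ratio | Paired CI / mean-baseline CI | Type I error, large sample | Type I error, N = 20 |
|---|---|---|---|---|
| 0.9 | 0.975 | 1.026 | 5.6% | 5.5-5.8% |
| 0.8 | 0.949 | 1.054 | 6.3% | 5.9-6.3% |
| 0.6 | 0.894 | 1.118 | 8.0% | 7.5-7.8% |
| 0.5 | 0.866 | 1.155 | 9.0% | 8.5-8.8% |
| 0.3 | 0.806 | 1.240 | 11.4% | 10.5-11.0% |

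The large-sample column is 2 × (1 − Φ(1.96 × SE ratio)). Applying the drop-group rule with equal groups gives about 5.7%, 6.4%, 7.6%, 8.6% and 11.0%, so that rule hardly changes the result. The paired t-test on the same data gives about 5% in every row.

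**Unequal SDs, N = 20, r = 0.9, 0.8, 0.6, 0.5, 0.3.**

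- k = 0.9: 7.6%, 7.8%, 9.3%, 10.4%, 13.0%.
- k = 1.2: 5.2%, 4.9%, 5.8%, 6.6%, 8.2%.

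At k = 1.2 and r = 0.8 the slope is 0.96. The ratio is √(1.44 × 0.36 / (2.44 − 1.92)) = √(0.5184/0.52) = 0.998, so almost nothing is lost. At k = 1.25 and r = 0.8 the slope is exactly 1, the ratio is 1.000 and the simulated error is 4.8% at N = 20.

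**Uncentred intercept.** This parameter is the change at baseline 0. With no mean change and equal SDs its expected value is (1−r) × mean baseline, which is not zero. It therefore does not test mean change.

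**The case against.** The best defence is that the plan shows an omission and not an error. Conditional on the baselines observed, the regression SE is correct. The study recruited a convenience sample, so inference to a population is uncertain under any method. Reporting a conditional effect would be defensible, but the plan would have to say so, and it does not. The point that the SE is too small therefore stands only for unconditional mean change.

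A reader might infer more in several ways that the documents do not support:

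- **That pairing was ignored.** Modelling within-person differences already uses the pairing. What is missing is a named parameter.
- **That the intercept was tested.** Nothing in the text shows this. With N = 20, a mean baseline of 3 SD and equal SDs, the intercept would reject in 15%, 26% and 49% of samples at r = 0.9, 0.8 and 0.6. Those are rejections of a different null hypothesis (change at baseline 0), and they should not set the weight of this point.
- **That the shortfall always grows as correlation falls.** This holds at equal SDs only. At k = 1.2 the SE ratio moves from 0.989 at r = 0.9 to 0.998 at r = 0.8. At k = 0.8 it moves from 0.780 to 0.800. What counts is the distance of the slope from 1 relative to residual variance.
- **That the plan's confidence intervals are too narrow.** The section mentions p-values and Cohen's d, and no confidence intervals.

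The defence is also right that the size is assumed and is small over part of the range: about one percentage point or less at equal SDs with r of 0.8 to 0.9.

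**Conclusion.** The concern holds in this limited form. It is certain that the tested parameter and the baseline value are not stated, and this affects all 28 continuous outcomes. It is also certain, by algebra, that the mean-baseline contrast understates the SE of population mean change unless the post-on-pre slope is 1. How much it does so in this trial is unknown.

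Under normal data, N = 20, equal SDs and no true change, type I error runs from about 5.6% (r = 0.9) to about 11% (r = 0.3), and it is close to 5% when the slope is near 1. The paired t-test holds 5% under the same normality assumption. It does not hold it under strong skew: with mean-zero exponential differences its error is 9.9%, 8.2% and 6.9% at N = 10, 20 and 40.

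This should be fixed, with medium confidence. It is more than missing detail, because neither candidate parameter gives a valid unconditional test of mean change unless the slope is 1. It does not show that any reported result is wrong.

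**What to change.** 1. State, for the analysis as run, which parameter gave the p-value for pre-post change and at what baseline value.
2. Test pre-post change for each continuous outcome as the paired mean change (an intercept-only model on the difference), and report it with its paired-t 95% CI.
3. Keep the baseline-adjusted model for comparing the two exercise groups.
4. Where differences are clearly skewed, say that the paired-t result is approximate and also show the median and IQR of the differences.
5. If results are already known, label the change post hoc.

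The cost is revised wording and a short rerun on data already collected. The downside is that intervals would be about 3% (r = 0.9) to 24% (r = 0.3) wider than the mean-baseline version at equal SDs, so some nominally significant results may be lost.

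### Time since stroke enters no analysis, so the comparison of the two exercise programmes may carry an unexamined difference in recovery stage

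*Combined protocol and SAP*

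**What the plan says.** - **Covariates.** The Statistical analysis section states: "Treatment group (Endurance only vs Endurance plus transference) and baseline measures were included as covariates". No other covariate is named.
- **Meaning of baseline measures.** The preceding paragraph of that section uses the term for the quantities whose change is analysed: "differences in baseline measures from pre-treatment to post treatment were calculated, including EAT-10 scores", then the IOPI, MBSImP, SWAL-QOL and ASPEKT measures. Time since stroke is not listed.
- **Entry rule.** The opening Study Protocol paragraph requires "at least 3 months since initial ischemic stroke" and sets no upper limit.
- **Design, sampling and allocation.** Study Visits says: "This study used a prospective quasi-experimental design, with pre-test and post-test measures". Study Protocol says: "A convenience sample of participants were recruited from word-of-mouth referrals". On allocation, Study Visits says only: "Half of the participants were instructed to complete this task 2 times a day and once a day to do 10 effortful swallows". How that half was chosen is not described, and neither matching, stratification nor an untreated control is mentioned.
- **Interval between measurements.** The baseline visit is "followed by 8-10 weeks of at home lingual exercise with use of the TongueometerTM device".
- **Model reduction.** "Treatment group effects that were not statistically significant were eliminated from the model and re-evaluated".

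**The concern.** With a 3-month minimum and no maximum, the sample may mix people a few months after stroke with people many years after it. Their expected change over 8 to 10 weeks may differ whatever exercise they do. Adjusting for the outcome's baseline value does not remove that difference, because two people with the same EAT-10 score can be at different stages of recovery.

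Two results are affected.

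- **Group coefficient.** If the two halves differ in time since stroke, the coefficient mixes programme with recovery stage. The reduction rule adds to the consequence. Confounding could produce a group effect that is kept, or hide one so that the term is dropped and the programmes are pooled in a model adjusted for baseline alone.
- **Average pre-to-post change.** It is reported as one figure. With no untreated control, whether change is also seen in participants long after stroke is one of the few things these data can say about recovery as an explanation. The plan does not look.

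**Working it through.** **What can be reproduced.** The documents state no sample size, SD, effect size or power, so there is no planned figure to check. The omission is established by reading: time since stroke appears in the eligibility sentence and then in no model, subgroup or sensitivity analysis. Everything below illustrates size on assumed inputs.

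**Step 1. Bias in the group coefficient.** Assumptions: given baseline, change falls by b residual SDs per log-unit of time since stroke, and the geometric mean time is 6 months in one half and 12 in the other.

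Bias = b × ln(12/6) = b × 0.693.

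- b = 0.2: 0.14 SD
- b = 0.3: 0.21 SD
- b = 0.5: 0.35 SD

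With no imbalance the bias is zero.

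**Step 2. Effect on the nominal 0.05 test of group.** Let D be the imbalance in SDs of log time and ρ the slope per SD, with residual SD 1. With m participants per group, the test without time since stroke follows a noncentral t with 2m−3 degrees of freedom and noncentrality ρ × D × √(m/2). Type I error (two-sided):

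| m per group | ρ=0.3, D=0.5 | ρ=0.3, D=1.0 | ρ=0.5, D=0.5 | ρ=0.5, D=1.0 |
|---|---|---|---|---|
| 5 | 0.055 | 0.070 | 0.064 | 0.106 |
| 10 | 0.062 | 0.097 | 0.083 | 0.184 |
| 20 | 0.075 | 0.152 | 0.120 | 0.338 |

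At D = 0 it is 0.05 throughout. The twofold imbalance of step 1 with a log-SD of 1 is D = 0.69, between the columns.

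**Step 3. Cost in precision with chance imbalance only.** If time since stroke explains a share R² of the residual variance, the ratio of group interval widths (with the covariate to without, total sample n) is about

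√(1−R²) × √(1+1/(n−5)) × t(n−4)/t(n−3), using 97.5% points of t.

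- n=20, R²=0: 1.0328 × 2.1199/2.1098 = 1.038, about 4% wider. At R² of 10%, 20% and 30% it is 2%, 7% and 13% narrower.
- n=10, R²=0: 1.0954 × 2.4469/2.3646 = 1.134, about 13% wider.
- n=8, R²=0: 1.1547 × 2.7764/2.5706 = 1.247, about 25% wider. Even at R²=30% it is about 4% wider.

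**Step 4. Cost when the imbalance is systematic.** The bias in step 1 needs a systematic imbalance, so its cost must be computed under the same imbalance. A systematic difference D multiplies the width by about a further √(1+D²/4). With log-SD 1, D = 0.693 and the factor is √(1+0.4805/4) = 1.058. At R²=0:

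- n=20: 1.038 × 1.058 = 1.098, about 10% wider.
- n=10: 1.134 × 1.058 = 1.200, about 20% wider.

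Simulation with equal groups and a baseline covariate gives the same 10% and 20%. At n=20 and R²=0 it gives about 17% for a log-SD of 0.7 and about 8% for 1.3. With log-SD 1 at n=20, the interval is still about 5% wider at R²=10% and about 1% narrower at R²=20%.

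**The case against.** **The imbalance is not shown, and the allocation method is unknown.** A reader might infer that the programmes were assigned non-randomly and that the halves differ in recovery stage. The documents support neither as a fact. The term quasi-experimental may refer only to the missing untreated control. What stands is narrower: no protection against imbalance is described, and the analysis neither displays nor adjusts for it.

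**The variable may not be on file.** A reader might infer that the exact interval is already recorded. The entry rule is a threshold: it implies that onset is known well enough to apply it, no more. It also counts from the initial ischemic stroke, and recurrent stroke is not excluded, so the interval may measure recovery stage imperfectly. Both points stand as limits.

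**The precision cost is not negligible.** It depends on a sample size that the documents do not give and grows with the imbalance that motivates the adjustment. This stands, and it is why a very small sample calls for a sensitivity analysis.

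**Why this covariate?** Age, stroke severity and adherence are also left out, and the plan favours parsimony across 28 change outcomes (1 EAT-10, 8 IOPI, 2 MBSImP, 5 SWAL-QOL, 12 ASPEKT). That is fair against a long covariate list, less so against one term that the protocol itself makes an entry condition and that bears on the recovery explanation.

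**Could the plan already cover it?** The outcome list is introduced by the word including, so baseline measures might be read more widely. But the listed items are measures with a pre-to-post difference, and time since stroke is not an outcome of that kind. The general promise of descriptive statistics might tabulate it, but would not relate it to change.

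**Adjustment cannot isolate the treatment effect.** True. Without an untreated control, recovery, practice and regression to the mean all remain.

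**Conclusion.** The point holds as an avoidable gap in the analysis. The change models adjust only for group and baseline outcome values, time since stroke is used nowhere, and no design feature is described that would balance it. The group coefficient may therefore reflect recovery stage as well as programme.

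The size cannot be taken from the documents. A bias of 0.14 to 0.35 SD rests on assumed slopes and an assumed twofold imbalance; with no imbalance or no slope it is zero. Type I error for the group test runs from 0.05 with no imbalance to 0.184 at 10 per group in the most adverse scenario shown, and 0.338 at 20 per group.

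Two stronger conclusions should not be drawn: that the reported group comparison is in fact confounded, and that adjustment would separate exercise from natural recovery. The first needs data that the documents do not contain; the second needs a control group that the design does not describe.

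**What to change.** 1. Show time since stroke, counted from the initial ischemic stroke as in the entry rule, by group in the baseline table. If the exact interval was not recorded, retrieve the onset date.
2. For each change outcome, pre-specify one adjusted analysis: group, baseline value of the outcome, and centred log time since stroke. Keep the time term whatever its p-value. Keep the group term in this analysis whatever its p-value as well; otherwise the rule that removes non-significant group effects would delete the coefficient to be reported.
3. Report the adjusted group coefficient, and the predicted mean change with 95% CI at the sample mean and at the upper quartile of time since stroke. State that the second prediction relies on a log-linear relation.
4. If the sample is very small, present this as a sensitivity analysis beside the stated model.
5. State that the adjustment does not replace an untreated control. The section is written in the past tense; if the analyses are already complete, label the addition post hoc.

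**Cost.** A few sentences in the plan, one baseline row, one covariate, one degree of freedom and possibly a wider group interval, by the amounts in steps 3 and 4 of the working. Where the imbalance is real, that widening is the price of removing the bias.

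### Dropping the treatment-group term when it is not significant pools two different programmes without evidence of equivalence; the average pre-post change survives, the programme comparison does not

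*Combined protocol and SAP*

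**What the plan says.** Under Study Visits, the general instruction is "Participants were assigned to complete this task 3 times per day", followed by a variant: "Half of the participants were instructed to complete this task 2 times a day and once a day to do 10 effortful swallows". The sample therefore contains two programmes that share two of three daily sessions.

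Under Statistical analysis, the change models are specified as "Treatment group (Endurance only vs Endurance plus transference) and baseline measures were included as covariates". Two sentences then govern the group term: "Models were evaluated for parsimony" and "Treatment group effects that were not statistically significant were eliminated from the model and re-evaluated". The only threshold given is "Statistical significance was determined at p-values less than 0.05". I take that as the elimination criterion, two-sided, with one model per change outcome; neither is spelled out.

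No sample size, SD, target difference or equivalence margin appears anywhere. Nothing says whether the estimate and interval for an eliminated group term are reported. Cohen's *d* is mentioned ("d was used to calculate effect sizes") without saying for which contrast, so it does not settle that question.

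**The concern.** Removing a term because p is at least 0.05 treats a difference that was not detected as one that is absent. Three things follow for the programme comparison:

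- A p-value decides, outcome by outcome, which models keep a programme contrast. Unless the eliminated estimates and intervals are shown, a reader cannot tell a real absence of difference from too little data.
- If only the surviving contrasts are shown, they overstate a real difference on average, because only large estimates pass the filter.
- Once group is gone, the model gives both programmes the same adjusted change. Anyone who reads that pooled interval as the result of one programme gets an interval centred in the wrong place whenever the programmes differ.

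The study names two programmes and tests the term that separates them, so these readings are foreseeable even though the main question is average change.

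**Working it through.** **Inputs from the documents.** Two programmes with half the participants in each (Study Visits); change regressed on group and baseline, threshold 0.05, group dropped if not significant (Statistical analysis). Listed change outcomes: EAT-10 1 + IOPI 8 + MBSImP 2 + SWAL-QOL 5 + ASPEKT 12 = 28. There is no planned figure to reproduce.

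**Assumptions.** Total N of 16, 20, 30 or 40, with 128 for contrast; 1:1 split; true group difference *d* from 0 to 0.8, in residual SD; baseline slope −0.2; normal errors. Each setting was simulated 40,000 times, comparing the rule (drop group if p ≥ 0.05 and refit) with group always kept.

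**Step 1: average change.** A least-squares fit evaluated at the covariate means equals the sample mean change. With equal groups this is also the equally weighted average of the two programmes, so the estimate is identical with or without group. Simulated 95% CI coverage is 94.7–95.2% under the rule and 94.8–95.3% with group kept. Mean widths differ by at most about 1.5%.

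**Step 2: what the group test can exclude.** Ignoring chance baseline imbalance, the CI half-width for the difference is t(0.975, N−3) × 2/√N. At N=20 this is 2.110 × 0.447 = 0.94 SD; the simulation, which includes the imbalance, gives 0.96.

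**Step 3: how often a real difference is dropped.** The noncentrality is d√N/2. At N=20 and d=0.5 it is 0.5 × 4.472/2 = 1.118, giving power of about 18% and hence elimination about 82% of the time.

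**Step 4: why survivors are exaggerated.** At N=20 an estimate must exceed roughly 0.94 SD to be kept. Against a true 0.5 SD that is already 0.94/0.5 ≈ 1.9 times the truth; the average survivor is larger still.

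| Simulated result | N=16 | N=20 | N=30 | N=40 | N=128 |
|---|---|---|---|---|---|
| Mean CI half-width for group difference (SD) | 1.10 | 0.96 | 0.76 | 0.65 | 0.35 |
| Programmes identical, group dropped: CI still reaches 0.8 SD in a direction | 99% | 97% | 85% | 62% | 0% |
| Group dropped, d=0.5 | 86% | 82% | 74% | 67% | 20% |
| Group dropped, d=0.8 | 70% | 63% | 46% | 32% | 1% |
| Mean kept estimate ÷ truth, d=0.5 | 2.4 | 2.3 | 1.9 | 1.7 | 1.1 |
| Mean kept estimate ÷ truth, d=0.8 | 1.7 | 1.5 | 1.3 | 1.2 | 1.0 |

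**Step 5: reading the pooled result as one programme's.** When group is dropped, each programme's true mean lies d/2 from the pooled mean. At d=0.5 that is 0.25 SD, against a pooled standard error of about 1/√20 = 0.22 SD at N=20. Coverage of the rule's interval for a programme's own mean, for N=16–40, is:

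- 93% at d=0
- 89.5–92% at 0.2
- 85–90% at 0.3
- 80–88% at 0.4
- 74–85% at 0.5–0.8 (84% at N=20, d=0.5)

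With group kept it is about 95% throughout.

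**Step 6: accuracy of each programme's mean (RMSE, rule vs group kept).**

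| d | N=20 | N=40 |
|---|---|---|
| 0.2 | 0.273 vs 0.321 | 0.206 vs 0.225 |
| 0.3 | 0.295 vs 0.320 | 0.233 vs 0.225 |
| 0.5 | 0.350 vs 0.321 | 0.282 vs 0.226 |

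**Step 7: across outcomes.** With no true difference anywhere, 28 × 0.05 = 1.4 models would be expected to keep group by chance. If the outcomes were independent, the probability of at least one is 1 − 0.95^28 = 76%. Model form would then differ between outcomes for no substantive reason.

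**The case against.** The strongest reply is that this is a pre-test/post-test study whose models address change over time, with group only a covariate. The section introduces its outcomes that way: "To examine treatment effects, differences in baseline measures from pre-treatment to post treatment were calculated". The plan never says that non-significance means equivalence, never says eliminated contrasts go unreported, and never proposes to read a pooled interval as one programme's own. The elimination probabilities are simply the type II error of a valid 0.05 test, and the wide intervals come from small (assumed) samples; keeping group cures neither. If the programmes differ by only about 0.2 SD, which is plausible given the shared sessions, pooling estimates each programme's mean with less error.

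Much of this stands. The main question is not damaged under an equal split, and the plan is silent on reporting rather than shown to omit anything. The trade-off at small differences is real. What remains is that the elimination rule is stated outright, the two programmes are named, and no margin, sample size or reporting rule makes a non-significant result informative. The plan offers no basis for assuming the small-difference case. Keeping group does not narrow the interval for the difference; it makes the uncertainty visible.

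The claim that average change is unaffected also depends on balance, and completers per programme are not given. With an assumed 70/30 split at N=20, coverage for the equally weighted average falls to 92–93% under the rule (d=0.5–0.8), against 95% with group kept.

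**Conclusion.** The concern holds. It is a flaw in a stated analysis rule that should be fixed, confined to the programme contrast and programme-specific statements. For totals of 16 to 40, a true difference of 0.5 SD would be eliminated 67–86% of the time, surviving estimates would average 1.7–2.4 times the truth, and the rule's interval read as one programme's own would cover 76–85% of the time instead of 95%. Even at N=128 the rule's coverage for a programme's own mean is only about 81% at 0.5 SD.

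These sizes rest on assumed N, residual SD units, baseline slope, an equal split and one model per outcome. The qualitative point, that elimination is not evidence of equivalence, does not depend on them. At a true difference of about 0.2 SD the loss of coverage is small and pooling has the lower error.

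**What to change.** Replace the elimination sentence with:

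> Treatment group and the outcome's own baseline value are kept in the linear model for every change outcome, whatever the p-value. For each outcome we report n per programme, the average pre-post change across programmes, the adjusted change in each programme and the adjusted group difference, each with a 95% CI. A non-significant group effect is not reported as no difference.

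The average change should be computed as the mean of the two adjusted programme means at the mean baseline (LSMEANS or ESTIMATE in SAS). The raw intercept of a 0/1-coded model should not be used, because it describes the reference programme only.

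The cost is one sentence, a rerun on existing data and one residual degree of freedom per model. At N=20 with no true difference, the mean half-width for the average change is 0.465 SD with group kept and 0.460 under the rule. Programme-specific intervals do widen: at N=20, 0.67 instead of 0.47 SD at a true difference of 0.2 SD, and 0.67 instead of 0.50 SD at 0.5 SD. If the true difference is about 0.2 SD or less, each programme's mean is estimated with more error than by pooling; that is the price of intervals with their stated coverage.
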